# 10.2.3. Methods/Timing for Assessing, Recording, and Analyzing Safety Endpoints

AEs will be assessed at study visits starting after the first administration of investigational product until the final follow-up visit. However, SAEs will be collected from the time of informed consent onward. General symptoms will be collected via an open-ended question: "How have you been feeling since your last visit or the last time we spoke?"

AEs will be documented in the source records and recorded on the eCRFs using accepted medical terms and/or the diagnoses that accurately characterize the event. When a diagnosis is known, the AE term recorded on the eCRF will be the diagnosis rather than a constellation of symptoms. The investigator will assess all AEs for seriousness, relationship to investigational product, and severity. When an event has not resolved by study closure, it will be documented on the AE eCRF as "ongoing".

If a woman has a positive pregnancy test after enrollment, the NIAAA Medical Monitor will be contacted and the pregnancy will be recorded as an AE. The site will contact the subject at least monthly and document the subject's status until the pregnancy has been terminated or completed. The outcome of the pregnancy will be reported to the NIAAA Medical Monitor without delay within 24 hours of knowledge of the event if the outcome is a SAE (e.g., death, abortion, congenital anomaly, or other disabling or life-threatening complication to the mother or newborn).

All AEs, including clinically significant abnormal findings on laboratory evaluations, regardless of severity, will be followed by study physicians until satisfactory resolution (the event either resolved or stabilized and is not expected to resolve in the near term). AEs must be reported up to 2 weeks following completion of, or termination from investigational product administration. At the follow-up telephone contact, AEs will be recorded and followed to resolution only if they are serious, or if the study physician assesses them to be clinically significant.

## 10.2.4. Clinical Laboratory Abnormalities and Other Abnormal Assessments

Abnormal clinical laboratory findings (e.g., clinical chemistry) will be reported as an AE unless the value was outside normal laboratory limits at baseline and did not increase by a severity grade level at the follow-up assessment. Grade 2 or greater hypokalemia and Grade 3 or greater results for any other laboratory test will be considered clinically significant. Likewise if blood pressure was elevated at baseline [pre-hypertension (systolic BP 120 - 139 mmHg or diastolic BP 80 - 89 mmHg)] and increased to a level indicative of an increase in the severity grade, hypertension will be reported as an AE.

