Note: The MINI suicidality module rates scores of 1 to 8 as a diagnosis of low risk of suicidality. As the MINI questions that could result in a low risk score are considered inadequate to fully determine the potential suicidal risk of an individual (e.g., "Feel hopeless" and "Think that you would be better off dead or wish you were dead?" responses of "yes" dictates a score of 1 for each question), any subject who scores in the low risk category should be evaluated further by a study physician or psychologist who should document whether the subject is appropriate for study inclusion based on his/her clinical judgment of the potential suicide risk of the subject. Likewise, if the subject responds "yes" to either of the first two questions on the screening C-SSRS performed on the day of randomization as a final eligibility check, the subject should also evaluated by a study physician for current suicidality risk, who should document the subject's suitability for study inclusion.

- 15. Have moderate or serious dementia as assessed by clinical exam.
- 16. Be pregnant or breast-feeding or have plans to become pregnant at any time during the study.
- 17. Have clinically significant abnormal liver enzyme levels defined as AST or ALT 5-fold above the upper limit of normal (ULN), or bilirubin greater than 2 times the ULN.
  - Note: If the subject has values of liver enzyme that are 3.0-to-4.9 fold above the ULN and bilirubin that is 1.5-to-1.9 fold above the ULN of normal, these assessments should be repeated at least a week apart and if still in this range or higher, the subject should be excluded from the study and referred to their physician for further follow-up.
- 18. Have sodium < 132 mmol/L or > 150 mmol/L or potassium < 3.2 mmol/L or > 5.5 mmol/L or abnormal calculated creatinine clearance (<60 mL/min), as calculated by Cockcroft and Gault formula.
- 19. Have a serious or unstable medical illness or any potentially life-threatening or progressive medical condition other than addiction that may compromise subject safety or study conduct.
- 20. Have clinically significant gastrointestinal, neurological, renal, or cardiovascular disease such cardiac arrhythmia, uncontrolled hypertension, congestive heart failure, or any other ECG abnormality considered clinically significant by the PI.
- 21. Have data suggesting cirrhosis of the liver.

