#### **10.2.1.** Adverse Event Definition

An AE is any untoward medical occurrence in a patient or clinical investigation subject administered a pharmaceutical product and may not necessarily have a causal relationship with the administered treatment. An AE can therefore be any unfavorable and unintended sign (including a clinically significant laboratory abnormality), symptom, or disease temporally associated with the use of an investigational product, whether or not related to the investigational product. Pre-existing conditions, diseases, or disorders are not considered AEs unless there is a change in severity or frequency.

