# 10.7. Clinical Chemistry

Clinical laboratory tests will be performed at the clinical site's local clinical laboratory. Laboratories performing these assessments should be directly regulated by the College of American Pathologists (CAP) or Clinical Laboratory Improvement Act (CLIA) guidelines. The laboratory will need to provide a copy of current certification. Additional laboratory samples may be taken at the discretion of the investigator if the results of any tests fall outside reference ranges or clinical symptoms necessitate testing to ensure safety. Clinical chemistry tests are listed below.

- Creatinine
- Total bilirubin
- Alanine aminotransferase (ALT)
- Aspartate aminotransferase (AST)
- Sodium
- Potassium

Serum creatinine levels will be used to calculate creatinine clearance (CrCl) according to the Cockroft-Gault (1976) formula as follows:

Males  $CrCl (mL/min) = \frac{(140 - age in years) \times body \text{ weight in kg}}{72 \times serum \text{ creatinine mg/dL}}$ Females  $CrCl (mL/min) = \frac{0.85 \times (140 - age in years) \times body \text{ weight in kg}}{72 \times serum \text{ creatinine mg/dL}}$ 

For any laboratory test value outside the reference range that the investigator considers clinically significant:

- The investigator will repeat the test to verify the out-of-range value
- The investigator will follow the out-of-range value to a satisfactory clinical resolution
- A laboratory test value will be reported as an AE with the severity score assigned in accordance with the CTCAE version 5.0

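### Protocol 10.2.4 and 10.7 set different triggers for recording a laboratory value as an AE, so new Grade 1 hyponatremia may be counted at some sites and not at others

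*Protocol*

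**What the plan says.** Four places in the protocol bear on whether a laboratory value becomes an AE.

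- Section 10.2.4 gives a rule that needs no judgement: "Abnormal clinical laboratory findings (e.g., clinical chemistry) will be reported as an AE unless the value was outside normal laboratory limits at baseline", with the exception applying only if the value also failed to rise by a severity grade.
- The same section then defines a separate term: "Grade 2 or greater hypokalemia and Grade 3 or greater results for any other laboratory test will be considered clinically significant".
- Section 10.7 opens its list of actions with a condition, "For any laboratory test value outside the reference range that the investigator considers clinically significant". Under that condition come repeating the test, following the value to resolution, and a third bullet: "A laboratory test value will be reported as an AE with the severity score assigned in accordance with the CTCAE version 5.0".
- Section 10.2.1 defines an AE as "any unfavorable and unintended sign (including a clinically significant laboratory abnormality), symptom, or disease temporally associated" with use of the product.

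Table 6 in Appendix B makes hyponatremia Grade 1 from the lower limit of normal (LLN) down to 130 mmol/L, has no Grade 2, and starts Grade 3 below 130. Laboratories are local (10.7) and there are four sites.

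SAP 9.6.1 tabulates recorded AEs and adds no rule for laboratory values. For chemistry, SAP 9.6.2 and shell Table 106 plan descriptive statistics and change from baseline. Listing 32 shows each value with a high/low flag and a clinical-significance evaluation. Protocol 11.4.4 also promises chemistry shift tables; neither SAP 9.6.2 nor the shells contain them.

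**The concern.** The two reporting rules part exactly where the drug's known signal lies. Protocol 4.3 names hyponatremia as a risk of intranasal oxytocin. Protocol 4.1.6 reports that three oxytocin subjects in the earlier 12-week AUD trial had mild, transient, asymptomatic hyponatremia. A mild case of that kind, if Grade 1, is an AE under 10.2.4. Under 10.7 it is an AE only if the investigator calls it clinically significant, and the one definition of that term in the protocol guarantees it for sodium only from Grade 3.

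Because the AE tables count what sites enter, the tabulated frequency of mild hyponatremia would depend partly on which section each site follows. With 50 subjects per arm there is little room to lose events in a safety comparison, and the missing shift tables remove the count that would have been independent of the AE entries.

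**Working it through.** The documents state no hyponatremia rate for this trial, so there is no figure to reproduce. The check has two parts.

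**1. Apply both rules to the same sodium values.** Grades are from Table 6. Entry requires sodium of at least 132 mmol/L (7.3.2, item 18: "Have sodium < 132 mmol/L" excludes). The local LLN is not given; 133, 135 and 136 are assumed. For 10.7, the column shows only what the Grade 3 threshold in 10.2.4 makes automatic; below that, the investigator decides.

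| Assumed LLN | Baseline | Follow-up | AE under 10.2.4 | Automatically significant, so AE under 10.7 |
|---|---|---|---|---|
| 135 or 136 | 138 | 134 to 130 | yes | no |
| 133 | 134 or 138 | 132 to 130 | yes | no |
| 135 or 136 | 132 or 134 | 134 to 130 | no (Grade 1 at baseline, no worsening) | no |
| any of the three | any of the three | 129 | yes | yes |

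The rules agree on Grade 3 and differ on new Grade 1 cases. A subject who enters between 132 and the local LLN and stays in Grade 1 is not an AE under 10.2.4 either.

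**2. Illustrate the size.** Inputs: 3 of 12 oxytocin subjects (4.1.6), 50 per arm and four sites (4.2). Assumptions: equal site sizes; the three mild cases were Grade 1 (no sodium values are given); sites not following 10.2.4 record no Grade 1 case, which is the extreme.

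- Rate: 3/12 = 25%; Clopper-Pearson 95% CI 5.5% to 57.2%. Among 50 subjects that is 12.5 (50 × 0.055 = 2.7 to 50 × 0.572 = 28.6).
- Expected AEs on oxytocin when k of 4 sites follow 10.2.4: 50 × 0.25 × k/4.
- Power: two-sided Fisher exact test at 0.05, 50 per arm. The oxytocin AE rate is 0.25 × k/4; the placebo AE rate is 0 or 0.02 × k/4 (true placebo rates of 0% and 2%, assumed).

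| Sites following 10.2.4 | Expected oxytocin AEs | Power, placebo 2% to 0% |
|---|---|---|
| 4 | 12.5 | 0.93 to 0.99 |
| 3 | 9.4 | 0.78 to 0.93 |
| 2 | 6.3 | 0.46 to 0.61 |
| 1 | 3.1 | 0.07 to 0.09 |
| 0 | 0 | 0 |

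At a true oxytocin rate of 10%, power is only 0.19 to 0.38 even when all four sites follow 10.2.4. The loss from mixed reporting is therefore large only if the true rate is high.

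**The case against.** The strongest reply is that the sections can be read together. Section 10.2.4 is the one devoted to laboratory abnormalities and states an explicit rule; 10.7 could be taken as adding a duty to repeat and follow. That reading is sensible, but no text makes it the rule, and 10.7 is a natural place for a site to look when a chemistry result comes back.

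Several stronger inferences are tempting and not supported:

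- *That the other sections limit AEs to clinically significant values.* Section 10.2.1 gives such a value as an inclusive example, and 10.7 is silent on values not judged significant. Only 10.7 is in real tension with 10.2.4.
- *That the reported rate of mild hyponatremia can run from all cases to none.* Grade 3 is a floor for clinical significance; an investigator may judge 131 significant, especially for a named risk. At the other end, 10.2.4 captures only new or worsened cases. And it is the AE rate that varies: sodium is drawn at Weeks 6, 8, 10 and 13 whatever the AE rule, summarised by visit, and listed.
- *That one arm would be favoured.* Randomization is stratified by site, so mixed reporting dilutes both arms.
- *That the gap between the entry limit of 132 and the trigger for a repeat test is a contradiction.* An entry limit and an on-treatment trigger need not match. Repeats are allowed (7.8, 10.7), and any value recorded as an AE must be followed under 10.2.3. What does need reconciling is that 10.7 makes a repeat depend on clinical significance, while 10.2.3 makes follow-up depend on AE status, which is the disputed point.

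The 25% also deserves caution. It comes from one 12-subject arm. Protocol 4.3 calls hyponatremia infrequent, the 13-week constipation trial (29 oxytocin subjects) saw no electrolyte effect, and 4.1.9 cites further studies without chemistry changes. That sites will differ is a risk and not a documented fact; training, monitoring and the Medical Monitor all work against it, and the Manual of Operations is not available here.

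**Conclusion.** The inconsistency is real and worth correcting before the data are unblinded. Sections 10.2.4 and 10.7 give different AE triggers, and new Grade 1 hyponatremia is where they differ. The likely effect is a lower and less interpretable AE-table rate in both arms. It matters beyond wording because hyponatremia is a named risk and, with the shift tables missing from the SAP, the AE tables are the only planned incidence count.

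The size cannot be fixed from the documents. With the 3/12 rate, equal sites and the extreme behaviour at non-following sites, two sites of four would halve the expected count, from 12.5 to 6.3, and cut power from 0.93–0.99 to 0.46–0.61. With a lower true rate, or with investigators who flag mild cases, the effect shrinks.

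**What to change.** In the protocol:

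- State that the rule in 10.2.4 is the single trigger for laboratory AEs. Reword the third bullet of 10.7 and the parenthesis in 10.2.1 to refer to it.
- Keep clinical significance as a separate recorded judgement; Listing 32 already has the field.
- Have the sponsor reconcile the repeat and follow-up wording in 10.2.3 and 10.7. No clinical threshold is proposed here.
- Use one CTCAE version: 10.2.5 and 10.7 cite 5.0, Appendix B cites 4.03.

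In the SAP, restore the chemistry shift tables in 9.6.2 and add a shell, so that low sodium is counted by grade from the laboratory data. State whether unscheduled draws enter that count, since 9.6.2 now leaves those taken between scheduled visits in the listings only. This part uses values already collected, so it protects the count even for subjects treated before sites receive clarification.

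The cost is a short amendment, a memo to sites, and one SAP paragraph with its shell. The downside is more Grade 1 laboratory AE entries, such as small ALT or AST rises, under the same rule in both arms.

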# 4.1.9. Safety of Multiple-Dose Intranasal Oxytocin

Studies of 1-4 Weeks Duration: Four studies provided safety information for oxytocin twice daily (BID) dose regimens of 1-4 weeks duration, with dose regimens ranging from 20 IU (Feifel-2010) to 72 IU (Finger-2015). In the 3 studies which listed specific AEs (Feifel-2010, Finger-2015, Parker-2017), those AEs that were reported in more than 1 patient included: inappropriate sexual behavior/ hypersexuality; sleep impairment; headache; dyspepsia /nausea; dizziness/lightheadedness; nasal irritation; and nasal congestion. There appeared to be no dose relationship with respect to any of these AEs. Nasal AEs (nasal irritation or nasal congestion) were the only AEs that were reported in more than 1 study (Feifel-2010, Parker-2017), and nasal discomfort from the intranasal spray was also a reason for 1 subject withdrawal (Feifel-2010). In one study in patients with dementia (*Finger-2015*), inappropriate sexual behaviour/ hypersexuality was reported in 5 (31%) of the 15 patients receiving oxytocin, compared with 1 (14%) of the 7 placebo patients (p = 0.4). However, there was no clear dose-response relationship, as this behaviour was seen only at the 2 lower doses of oxytocin (24 or 48 IU BID) and not at the highest dose (72 IU BID). Information on vital signs effects was available from 3 studies, with 2 of the 3 studies showing no oxytocin effect on vital signs (Finger-2015, *Pedersen-2011*), and the third study (*Parker-2017*) suggesting that systolic standing blood pressure increased in subjects treated with oxytocin 24 IU BID for 4 weeks. Oxytocin 24 IU - 40 IU BID for 2 weeks was not associated with changes in blood chemistry or urine parameters in two studies (*Pedersen-2011*, *Feifel-2010*).

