# 7.4. Eligibility Screening

After the subject undergoes alcohol breathalyzer testing and signs informed consent, screening may begin. During the first screening visit (additional visits are permitted if needed), subjects will undergo the following assessments:

- Demographics and locator form
- Urine drug screen
- Medical history
- Physical examination and body weight
- MINI
- Clinical chemistry
- Pregnancy test for females of childbearing potential and birth control methods, if female
- Vital signs
- ECG
- TLFB for the previous 28 days
- Prior medication use
- CIWA-AR
- Drinking goal
- UPSIT

Subjects will be instructed that if they are taking a medication for depression or anxiety that they should continue to do so throughout the study. They will also be instructed that they should report any new medications they are taking at each visit or telephone contract.

The above assessments can be performed in any order except that it is recommended to perform physical examinations including vital signs prior to blood draws. If any of these assessments reveal that the subject is not eligible for the study, screening can be immediately terminated and no further data be collected. Clinical chemistry tests may be repeated at the discretion of the investigator if the first assessment yields values outside normal laboratory limits. The eligibility checklist will be reviewed, and if the subject is still eligible after the assessments are completed at the first screening visit (or additional screening visits), the subject will be scheduled for the final eligibility check and baseline visit. It is recommended that hypertensive subjects be referred to their primary care physician for additional assessment and possible treatment, and then be further evaluated for study inclusion.

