# Appendix B. Common Terminology Criteria for Adverse Events for Clinical Laboratory Adverse Events and Elevated Blood Pressure

The following are the toxicity grades for which grading criteria are provided by the CTCAE (Version 4.03) for chemistry tests performed in this study and for elevated blood pressure (hypertension).

Table 6: CTCAE Criteria for Clinical Laboratory Adverse Events and Blood Pressure Elevations

Adverse Event	Grade 1	Grade 2	Grade 3	Grade 4
ALT elevated	>ULN – 3.0 x ULN	>3.0 – 5.0 x ULN	>5.0 – 20.0 x ULN	>20.0 x ULN
AST elevated	$>$ ULN $-3.0 \times ULN$	>3.0 - 5.0  x ULN	>5.0 – 20.0 x ULN	>20.0 x ULN
Total bilirubin elevated (bilirubinemia)	>ULN – 1.5 x ULN	>1.5 – 3.0 x ULN	>3.0 – 10.0 x ULN	>10.0 x ULN
Hypernatremia (elevated sodium)	>ULN - 150 mmol/L	>150 - 155 mmol/L	>155 - 160 mmol/L; hospitalization indicated	>160 mmol/L; life- threatening consequences
Hyponatremia (low sodium)	<lln -="" 130="" l<="" mmol="" td="">-	<130 - 120 mmol/L	<120 mmol/L; life- threatening consequences	</lln>	-	<130 - 120 mmol/L	<120 mmol/L; life- threatening consequences
Hyperkalemia (elevated potassium)	>ULN - 5.5 mmol/L	>5.5 - 6.0 mmol/L	>6.0 - 7.0 mmol/L; hospitalization indicated	>7.0 mmol/L; life- threatening consequences
Hypokalemia (low potassium)	<lln -="" 3.0="" l<="" mmol="" td=""><lln -="" 3.0
mmol/L; symptomatic; intervention indicated</lln>	<3.0 - 2.5 mmol/L; hospitalization indicated	<2.5 mmol/L; life- threatening consequences	</lln>	<lln -="" 3.0
mmol/L; symptomatic; intervention indicated</lln>	<3.0 - 2.5 mmol/L; hospitalization indicated	<2.5 mmol/L; life- threatening consequences
Creatinine elevated	>ULN - 1.5 x ULN	>1.5 - 3.0 x ULN	>3.0 - 6.0 x ULN	>6.0 x ULN
Hypertension	Pre-hypertension (systolic BP 120 - 139 mmHg or diastolic BP 80 - 89 mmHg)	Stage 1 hypertension (systolic BP 140 - 159 mmHg or diastolic BP 90 - 99 mmHg); medical intervention indicated; recurrent or persistent (24 hrs); symptomatic increase by >20 mmHg (diastolic) or to >140/90 mmHg if previously WNL; monotherapy indicated	Stage 2 hypertension (systolic BP≥160 mmHg or diastolic BP ≥100 mmHg); medical intervention indicated; more than one drug or more intensive therapy than previously used indicated	Life-threatening consequences (e.g., malignant hypertension, transient or permanent neurologic deficit, hypertensive crisis); urgent intervention indicated

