9.6.3 Vital Signs, Weight, and ECG

Vital signs will be presented as summary statistics and change from baseline. The percentage of ECG results considered abnormal and clinically significant will be provided. Body weight will be presented as summary statistics and change from screening. No statistical tests will be performed. Vital signs, ECG results, and weight measurements for all visits will be presented in the listings.

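### Protocol 10.2.4 makes hypertension a mandatory AE only when blood pressure was already elevated at baseline; new hypertension from a normal baseline is discretionary, and no SAP table counts it

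*Protocol*

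**What the plan says.** Protocol 10.2.4 has two reporting rules in one paragraph. For laboratory values: "Abnormal clinical laboratory findings (e.g., clinical chemistry) will be reported as an AE unless the value was outside normal laboratory limits at baseline". That exemption is lost if the value worsens by a grade. For blood pressure: "Likewise if blood pressure was elevated at baseline [pre-hypertension (systolic BP 120 - 139 mmHg or diastolic BP 80 - 89 mmHg". The trigger comes later in that sentence: "and increased to a level indicative of an increase in the severity grade, hypertension will be reported as an AE".

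Appendix B Table 6 grades hypertension as pre-hypertension (Grade 1), Stage 1 (Grade 2), Stage 2 (Grade 3) and life-threatening (Grade 4). Its Grade 2 cell includes "symptomatic increase by >20 mmHg (diastolic) or to >140/90 mmHg if previously WNL", so it provides for subjects who start normal.

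On entry, Protocol 7.4 says: "It is recommended that hypertensive subjects be referred to their primary care physician for additional assessment and possible treatment, and then be further evaluated". The purpose of this later evaluation is possible inclusion. Exclusion criterion 20 names only uncontrolled hypertension.

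On analysis, SAP 9.6.3 states: "Vital signs will be presented as summary statistics and change from baseline". No statistical tests are planned. The Table 102 shell gives N, mean, SD, median, maximum and minimum by arm and visit. Listing 36 gives individual values.

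**The concern.** The laboratory rule covers newly abnormal values and exempts only those already abnormal that did not worsen. The blood-pressure sentence opens with *likewise* but supplies only the worsening half. The smell-test rule in Protocol 10.34 supplies both halves: impaired scores are AEs, and a subject impaired at baseline has an AE on moving to a worse category. Blood pressure is the exception, which suggests a drafting gap.

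Vital signs are the first listed safety endpoint. Protocol 4.1.9 describes one short study "suggesting that systolic standing blood pressure increased in subjects treated with oxytocin 24 IU BID for 4 weeks". The evidence is mixed: the other two short studies with vital-signs data showed no effect, and neither did the 13-week study at 80 IU per day. The positive finding concerned standing pressure, whereas this trial measures sitting pressure (10.37). An open question of this kind calls for ascertaining the endpoint in the same way for everyone.

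**Working it through.** The plan states no figure on this point, so the check sets the rule against the grading table.

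**Step 1. Where the rule applies.** Take four baseline categories from Table 6 (normal, pre-hypertension, Stage 1, Stage 2) and count every move to a higher category, with Grade 4 as the top.

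| Baseline | Upward moves | Literal bracket | Bracket as lower bound of elevated |
|---|---|---|---|
| Normal | 4 | 0 | 0 |
| Pre-hypertension | 3 | 3 | 3 |
| Stage 1 | 2 | 0 | 2 |
| Stage 2 | 1 | 0 | 1 |
| Total | 10 | 3 | 6 |

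Read literally, the rule is silent on 10 − 3 = 7 moves; read generously, on 10 − 6 = 4, all from normal. One of those four is normal to pre-hypertension, which a sponsor may not want as an AE. The other three end at Grade 2 or above. These are counts of category moves, not of subjects.

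**Step 2. Examples.**
- 130/85 to 150/95, a rise of 20/10: pre-hypertension to Stage 1, mandatory.
- 110/70 to 150/95, a rise of 40/25: normal to Stage 1, discretionary.
- 145/92 to 165/102, a rise of 20/10: Stage 1 to Stage 2, mandatory only if the bracket is a lower bound.

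These use the numeric ranges. The Grade 2 cell also refers to recurrent or persistent elevation, so a single reading might not qualify.

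**Step 3. What covers the rest.** Protocol 10.2.1 counts any unfavourable, unintended sign or disease as an AE, and a pre-existing condition if its severity or frequency changes. New or worsened hypertension can be reported under it, but no blood-pressure level obliges this, and four sites may differ.

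**Step 4. What the SAP would show.** Table 102 has systolic and diastolic summaries, including change from baseline. Tables 90 to 98 count hypertension recorded as an AE. Listing 36 has the individual readings. None counts subjects by blood-pressure category, threshold or shift. Protocol 11.4.4 plans shift tables for clinical chemistry only.

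**The case against.** The strongest reply is that the sentence is a conditional. It says when hypertension will be reported and does not say that other hypertension will not be. On that view it merely clarifies the awkward case of an already abnormal baseline, and 10.2.1 handles everything else. This stands as far as it goes: such events are reportable. It does not remove the difference between a stated obligation for one baseline group and judgement for another.

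A reader might infer that a blood-pressure effect would be invisible in the SAP output. The documents do not support that. Change from baseline by arm in Table 102 does not depend on baseline category or AE reporting, a large rise enters the mean and may be the displayed maximum, and every value is listed. Only the count of subjects is missing.

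A reader might also want to state what share of events the rule loses. The documents give no baseline blood-pressure distribution, no event risk and no rate of reporting outside the rule. Risk is also unlikely to be unrelated to baseline: from 135 systolic, 140 is 5 mmHg away; from 110 it is 30.

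The Stage 1 part is the weaker one. The bracket may be meant as a lower bound, and exclusion criterion 20 and the referral in 7.4 probably keep that group small. Finally, descriptive reporting of vital signs is a legitimate choice, and the absence of a shift table is not in itself an error.

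**Conclusion.** The concern holds as an inconsistency in ascertainment. Hypertension reporting is mandatory only when pressure was already elevated at baseline and rose a grade. Normotensive baselines are outside the rule on either reading of the bracket; Stage 1 and Stage 2 baselines are outside on the literal reading. This is out of line with the laboratory rule beside it, the smell-test rule and Table 6.

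The AE incidence of hypertension will therefore depend partly on who was pre-hypertensive at entry and on investigator practice. With randomised, blinded arms the likelier result is under-counting in both arms, and so lower sensitivity, than a bias towards one arm. The size in subjects cannot be derived from the documents. The conclusion rests on the wording of 10.2.4 and on the SAP shells having no categorical blood-pressure table. It does not imply that such events are unreportable or that the SAP would hide a shift in mean pressure.

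**What to change.** 1. Reconcile Protocol 10.2.4 with Appendix B Table 6 so that the reporting rule covers every baseline category, including normal and Stage 1. The sponsor should set the reporting threshold and any persistence requirement. The CTCAE version should be settled in the same edit: 10.2.5 cites 5.0 and Appendix B cites 4.03.
2. In SAP 9.6.3 and Table 102, add a descriptive by-arm shift table of baseline against worst post-dose blood-pressure category, using the numeric ranges of Appendix B, as Protocol 11.4.4 already plans for chemistry. Name the baseline reading, since the Table 102 shell shows both screening and Week 1. No test is needed.
3. Correct the study weeks in the Listing 36 shell, which run to Week 27 and do not match this trial's visits.

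The cost is one protocol sentence and one table. No new data are needed, because blood pressure is already taken at every clinic visit, and the shift table is still possible if AE reporting cannot be changed retrospectively. The downside is perhaps a few more mild AEs in both arms.
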